## CONCLUSION

The challenges of topical medication use are widespread and well recognized across ophthalmology. The safety profile reported in this study, albeit a small sample size, indicates the dexamethasone intracanalicular insert is a safe alternative option to topical steroids to augment the anti-inflammatory properties of topical cyclosporine 0.05%. Further study is necessary but use of the dexamethasone insert may provide a means to optimize medication delivery without compromising safety or efficacy in the treatment of dry eye disease.

**Table 1 – Baseline Demographics**

Parameter	Dextenza + Cyclosporine N = 10	Loteprednol + Cyclosporine N = 11	Cyclosporine monotherapy N = 9
Age			
Mean $\pm$ SD (years)	56.6 $\pm$ 18.3	61.4 $\pm$ 11.6	61.1 $\pm$ 11.9
Race, n (%)			
White	8 (80%)	11 (100%)	6 (67%)
African American	2 (20%)	0	1 (11%)
Asian	0	0	2 (22%)
Gender			
Male / Female	4 M / 6 F	2 M / 9 F	1 M / 8 F
IOP			
Mean $\pm$ SD (mmHg)	6.6 $\pm$ 2.2	5.4 $\pm$ 1.5	5.7 $\pm$ 3.3

**Table 1.** Demographic and clinical characteristics. IOP = intraocular pressure; SD = standard deviation.

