5.1.1. Study Procedures

Screening/Prescription

After the patient has provided informed consent, the following information will be collected:

- Inclusion/exclusion
- Demographics
- Medical history and concurrent illnesses
- Concomitant medications
- UCVA and MR/BCVA as measured by ETDRS chart at 4m
- Ophthalmic Examination with dilation
- Intraocular pressure
- Meibomian gland assessment (expressibility and quality)
- DED Assessment
 - Schirmer's
 - MMP9
 - Osmolarity
 - Conjunctival injection
 - TBUT
 - Ocular surface staining (sodium fluorescein and lissamine green)
- Subject reported AE's
- Restasis BID OU prescription
- Lotemax BID OU for 1 month prescription
- DEXTENZA® insertion in one eye

- Insert Visualization
- Physician ease of insertion questionnaire
- DEQ-5 

Week 1, Week 2, Week 4 and Week 8

- UCVA and MR/BCVA as measured by ETDRS chart at 4m
- Concomitant Medications
- Ophthalmic Examination without dilation and with IOP
- Insert visualization
- Meibomian gland assessment (expressibility and quality)
- DED Assessment
 - Schirmer's
 - MMP9
 - Osmolarity
 - Conjunctival injection
 - TBUT
 - Ocular surface staining (sodium fluorescein and lissamine green)
- Subject reported AE's
- DEQ-5 

Week 12

- UCVA and MR/BCVA as measured by ETDRS chart at 4m
- Concomitant Medications
- Ophthalmic Examination without dilation and with IOP
- Insert visualization
- Meibomian gland assessment (expressibility and quality)
- DED Assessment
 - Schirmer's
 - MMP9
 - Osmolarity
 - Conjunctival injection
 - TBUT
 - Ocular surface staining (sodium fluorescein and lissamine green)
- Subject reported AE's
- DEQ-5 

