## **RESULTS**

### **Patient Demographics**

Sixty eyes of 30 subjects were successfully enrolled into the study including 20 eyes of 10 subjects in the dexamethasone/cyclosporine group, 22 eyes of 11 subjects in the loteprednol/cyclosporine group and 18 eyes of 9 subjects in the cyclosporine monotherapy group. All 3 groups were summarized by baseline characteristics, which are shown in Table 2.

None of the three groups, including the study and two control groups met the primary endpoint. In the dextenza group, the mean baseline corneal staining score was  $0.5 \pm 1.0$  with 70% ( $n=14$ ) without evidence of corneal staining at baseline. The mean score at weeks 4, 8 and 12 was  $0.6 \pm 1.0$  ( $P = 0.99$ ),  $0.5 \pm 1.1$  ( $P = 0.99$ ) and  $0.7 \pm 1.4$  ( $P = 0.97$ ), respectively. In the loteprednol group, the mean baseline corneal staining score was  $0.8 \pm 1.5$  with 64% ( $n=14$ ) without corneal staining at baseline. At weeks 4, 8 and 12, the mean score was  $0.9 \pm 0.9$  ( $P = 0.99$ ),  $0.0 \pm 0.0$  ( $P = 0.06$ ) and  $0.6 \pm 1.0$  ( $P = 0.78$ ), respectively. In the cyclosporine monotherapy group, the mean baseline corneal staining score was  $0.5 \pm 0.5$  with 50% ( $n=9$ ) of eyes absent of any corneal staining at baseline. There was no significant change in corneal staining at any time point with a mean score of  $1.1 \pm 1.4$  ( $P = 0.26$ ),  $0.3 \pm 0.6$  ( $P = 0.63$ ) and  $0.5 \pm 0.7$  ( $P = 0.99$ ) at weeks 4, 8 and 12, respectively. These results, in addition to comparisons of other outcome measures, are summarized in Table 3.

There was no significant change in conjunctival staining, Schirmer scores, TBUT, tear osmolarity or meibomian gland scores at any of the follow-up time points in comparison to baseline in all three groups. These results are summarized and also demonstrated in Table 3.

Across all visits, the mean IOP remained stable in all three groups. In the cyclosporine monotherapy group, there were no instances of IOP elevation  $>10$  mmHg above baseline. Similarly, in the dextenza and loteprednol groups, there were no instances of IOP elevation  $>10$

mmHg above baseline at any time point. There were no canalicular-related complications or adverse events related to implantation of the dexamethasone insert. No patients required removal of the insert.

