## DISCUSSION

This prospective, randomized, open-label clinical study evaluated the use of an intracanalicular 0.4 mg dexamethasone insert in combination with topical cyclosporine 0.05% for the treatment of dry eye. Although the efficacy of this combination remains unclear based on the results of this pilot study, the results of this study support the safety of this approach without any adverse events, no IOP spikes above baseline and no device-related complications.

Topical cyclosporine 0.05% has been shown to provide an improvement in tear production and dry eye-related symptoms but many patients in clinical trials leading to its approval reported a delay in symptomatic relief. As a delay in relief can contribute to reduced compliance, providers may initiate adjuvant use of topical steroids in combination with topical cyclosporine 0.05% and studies evaluating this combined regimen reported findings of quicker symptomatic relief and more rapid improvement of objective parameters such as Schirmer testing and corneal staining. No groups in this study met the primary endpoint, however, patients in the loteprednol group reported a significant improvement in symptoms as measured by the DEQ-5 questionnaire, consistent with prior studies evaluating the combined use of corticosteroids and topical cyclosporine 0.05%. The dextenza group also noted an improvement in symptoms, but the change was not statistically significant. An improvement in symptoms with a combination of cyclosporine 0.05% and corticosteroids corroborates what has previously been reported.

Several prior studies have highlighted the safety and efficacy of the dexamethasone insert evaluated in this present study with regards to postoperative pain and inflammation following cataract surgery. However, multiple recent studies have described use of the insert beyond the postoperative setting including a recent report describing the combined use of thermal pulsation therapy with the dexamethasone insert for the treatment of meibomian gland dysfunction. To our knowledge, this is the first study evaluating the adjuvant use of the dexamethasone insert in combination with cyclosporine 0.05%. Although this present study did not yield any significant results, we anticipate future studies will involve the dexamethasone insert evaluating its utility in the treatment of dry eye.

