**Table 2 - Results**

Parameter	Dextenza + Cyclosporine	Loteprednol + Cyclosporine	Cyclosporine monotherapy
Corneal staining			
• Baseline	0.6 ± 1.0	0.8 ± 1.5	0.5 ± 0.5
• 1 month	0.6 ± 1.0	0.9 ± 0.9	1.1 ± 1.4
• 2 month	0.5 ± 1.1	0.0 ± 0.0	0.3 ± 0.6
• 3 month	0.7 ± 1.4	0.6 ± 1.0	0.5 ± 0.7
Conjunctival staining			
• Baseline	0.5 ± 1.8	1.5 ± 1.8	0.4 ± 0.6
• 1 month	0.3 ± 0.6	0.9 ± 1.4	0.5 ± 0.7
• 2 month	0.4 ± 0.8	0.8 ± 1.8	0.3 ± 0.6
• 3 month	0.8 ± 1.7	1.0 ± 1.6	0.7 ± 1.4
Schirmer scores (mm/5 min)			
• Baseline	14.9 ± 10.3	10.3 ± 7.2	11.6 ± 10.5
• 1 month	15.4 ± 10.1	12.9 ± 9.1	10.1 ± 8.5
• 2 month	15.8 ± 9.4	12.4 ± 8.4	10.8 ± 6.4
• 3 month	12.3 ± 7.1	10.1 ± 6.0	9.6 ± 5.5
Tear breakup time (seconds)			
• Baseline	6.6 ± 2.2	5.4 ± 1.5	5.7 ± 3.3
• 1 month	8.0 ± 3.6	6.1 ± 2.8	7.4 ± 3.7
• 2 month	7.7 ± 3.1	6.2 ± 2.2	7.1 ± 3.4
• 3 month	7.7 ± 2.5	6.1 ± 2.4	7.3 ± 3.6
Tear osmolarity			
• Baseline	295.5 ± 17.4	311.3 ± 19.8	306.9 ± 28.4
• 1 month	304.4 ± 30.1	307.7 ± 17.3	307.9 ± 24.2
• 2 month	303.9 ± 22.1	300.1 ± 19.2	295.3 ± 20.7
• 3 month	299.5 ± 16.2	304.4 ± 28.7	304.6 ± 19.6
Meibomian gland scores			
• Baseline	8.7 ± 2.4	7.1 ± 2.1	9.2 ± 2.6
• 1 month	7.6 ± 1.8	6.7 ± 2.5	7.2 ± 1.4
• 2 month	8.3 ± 2.0	6.3 ± 2.6	8.2 ± 2.2
• 3 month	8.7 ± 2.0	6.0 ± 2.3	7.3 ± 1.4

**Table 2.** Results of clinical parameters are summarized with the mean and standard deviation demonstrated at weeks 4, 8 and 12 in comparison to baseline.

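### The baseline IOP row in SAP Table 1 repeats the baseline tear break-up time row figure for figure and cannot be relied on; separately, no follow-up IOP is printed, so the IOP safety statements cannot be checked.

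*SAP*

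**What the plan says.** The SAP is written as a report of the completed study. Its Table 1 carries the caption "Demographic and clinical characteristics. IOP = intraocular pressure; SD = standard deviation" and gives baseline IOP in mmHg for the three groups. Its Table 2 covers six parameters: corneal staining, conjunctival staining, Schirmer, TBUT, osmolarity and meibomian score. The caption reads "Results of clinical parameters are summarized with the mean and standard deviation demonstrated at weeks 4, 8 and 12 in comparison to baseline". IOP is not among the six.

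The protocol's schedule of events (Table 1) has IOP at all six visits. Protocol section 5.1.1 lists "Ophthalmic Examination without dilation and with IOP" at each follow-up visit.

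The SAP Results text makes two IOP statements. The first is "Across all visits, the mean IOP remained stable in all three groups". The second, made for the monotherapy group and then for the two steroid groups, is that "there were no instances of IOP elevation" of more than 10 mmHg over baseline. The Discussion shortens this to "no IOP spikes above baseline and no device-related complications". The Conclusion says the safety profile "indicates the dexamethasone intracanalicular insert is a safe alternative option to topical steroids".

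**The concern.** A row labelled in mmHg and a row labelled in seconds should not share three means and three SDs. If one was copied from the other, the only IOP mean and SD in the supplied SAP text is not IOP. A reader then cannot tell at what pressure the groups started or whether they were comparable.

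This matters because safety is the report's positive message. No group met the primary endpoint, and the Discussion calls efficacy unclear. IOP is one of the three grounds the Discussion gives for safety, beside adverse events and device complications. The SAP Introduction names raised IOP as a risk of long-term topical corticosteroids, and two of the three groups received a steroid. Both IOP statements rest on values that should be visible to the reader.

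**Working it through.** **Step 1: compare the two rows** (SAP Tables 1 and 2).

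| Group | Table 1, baseline IOP (mmHg) | Table 2, baseline TBUT (s) |
|---|---|---|
| Dextenza + cyclosporine | 6.6 ± 2.2 | 6.6 ± 2.2 |
| Loteprednol + cyclosporine | 5.4 ± 1.5 | 5.4 ± 1.5 |
| Cyclosporine monotherapy | 5.7 ± 3.3 | 5.7 ± 3.3 |

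Six of six figures match. Against the other five baseline rows of Table 2, the IOP row matches one of six for corneal staining (a single SD, 1.5) and none for conjunctival staining, Schirmer, osmolarity or meibomian score.

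**Step 2: could this be coincidence?** Suppose, generously, that IOP and TBUT had the same true mean and SD in every group. Assume also normal data and independence between groups, between measures and between each mean and its SD. The chance that a fresh sample reproduces all six figures to one decimal is the product over groups of P(mean agrees) × P(SD agrees). One million simulated samples per group gave:

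- n = patients (10, 11, 9): (0.0571 × 0.0754) × (0.0883 × 0.1167) × (0.0366 × 0.0474) ≈ 7.7 × 10⁻⁸
- n = eyes (20, 22, 18), treated as independent: (0.0816 × 0.1102) × (0.1243 × 0.1696) × (0.0515 × 0.0699) ≈ 6.8 × 10⁻⁷

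Coincidence is not credible.

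**Step 3: which row is the copy?** Identity shows only that one row came from the other. The TBUT baseline can be tested against its own follow-up in Table 2:

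| Group | Month 1 | Month 2 | Month 3 |
|---|---|---|---|
| Dextenza | 8.0 − 6.6 = +1.4 | 7.7 − 6.6 = +1.1 | 7.7 − 6.6 = +1.1 |
| Loteprednol | 6.1 − 5.4 = +0.7 | 6.2 − 5.4 = +0.8 | 6.1 − 5.4 = +0.7 |
| Monotherapy | 7.4 − 5.7 = +1.7 | 7.1 − 5.7 = +1.4 | 7.3 − 5.7 = +1.6 |

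Each change is 0.4 to 0.6 of the baseline SD, so the figures belong naturally to the TBUT series. The IOP row has no series behind it. The inference that the IOP row is the copy is strong, but it is not proof.

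**Step 4: what can be checked for IOP?** Table 2 prints weeks 4, 8 and 12 for every parameter it covers, and nothing at weeks 1 and 2 for any of them. By that format, IOP lacks 3 groups × 3 visits = 9 follow-up cells. No eye-level IOP value or largest rise is given either. The >10 mmHg statement is a count of individual rises, so it could not be checked from group means even with a correct baseline row. The copied row and the missing follow-up are therefore two separate gaps.

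The documents give no true baseline IOP, and none can be derived from them.

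**The case against.** The strongest reply is that this is a slip in one row of a demographics table. IOP is not a listed primary or secondary outcome in either document, and reporting it in a sentence is a legitimate choice. No test described under Statistical Analysis is shown to use baseline IOP, and no efficacy result changes. The count of rises may have come straight from correct records. All of this stands, and it limits the weight of the point. It does not restore the printed row, which remains the only IOP mean and SD supplied in a report whose conclusion is about safety.

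A second reply is that IOP data may sit elsewhere. The Results text calls the baseline table Table 2 and the results table Table 3, while they are printed as Tables 1 and 2. The contents correspond, so shifted numbering is the simpler reading. The point is limited to the supplied text, and the Table 1 row would need correcting in any case.

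A third is that the Discussion merely abbreviates a result whose threshold is given in the Results. That is fair. The wording is a minor matter, but as written it claims more than was reported.

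Two stronger readings are tempting, in opposite directions. A reader might infer that the IOP statements are false, or that TBUT was analysed as IOP. Nothing in the documents shows this, because a copied table row says nothing about the analysis file. A reader might instead infer from the zero count that the error is confined to the table. That does not follow either. Had TBUT stood in for IOP at every visit, mean changes of +0.7 to +1.7 would also have read as stable, and rises above 10 would probably have been few or none.

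**Conclusion.** The point holds in two separate parts.

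- **Copied row.** All six printed baseline IOP figures duplicate baseline TBUT. The IOP row is almost certainly the copy, and it should not be relied on. This rests on the exact match and on the coherent TBUT follow-up, not on any assumed true IOP.
- **No follow-up IOP.** None of the nine cells that Table 2's format would call for is printed in the supplied text, and there is no eye-level summary. The stability statement and the >10 mmHg statement cannot be checked. They are unverified, not refuted.

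Whether the error stops at the table or reaches the IOP analysis cannot be settled from the documents; only the source records can answer it. The correction should be made because the safety conclusion draws partly on IOP. It leaves the efficacy results untouched.

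**What to change.** 1. Replace the IOP row of SAP Table 1 with baseline IOP from source data. The values should not be guessed or back-calculated.
2. Confirm from eye-level records that both the stability statement and the >10 mmHg count used measured IOP at baseline and at follow-up. Re-run them only if they did not.
3. Report IOP mean and SD by group at least at baseline and weeks 4, 8 and 12. Weeks 1 and 2 would be a sensible addition, since the stability statement covers every visit.
4. Give the largest rise per eye, or the count and denominator of rises above 10 mmHg in each group, stating whether the unit is the eye or the patient.
5. In the Discussion, state the >10 mmHg threshold that the Results report.

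The cost is re-extraction of one variable already scheduled at every visit, one corrected row, one added IOP block and one reworded sentence. No new patients or visits are needed. Analysis is repeated only if step 2 finds that the wrong variable was used.

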**Table 2 - Results**

Parameter	Dextenza + Cyclosporine	Loteprednol + Cyclosporine	Cyclosporine monotherapy
Corneal staining			
• Baseline	0.6 ± 1.0	0.8 ± 1.5	0.5 ± 0.5
• 1 month	0.6 ± 1.0	0.9 ± 0.9	1.1 ± 1.4
• 2 month	0.5 ± 1.1	0.0 ± 0.0	0.3 ± 0.6
• 3 month	0.7 ± 1.4	0.6 ± 1.0	0.5 ± 0.7
Conjunctival staining			
• Baseline	0.5 ± 1.8	1.5 ± 1.8	0.4 ± 0.6
• 1 month	0.3 ± 0.6	0.9 ± 1.4	0.5 ± 0.7
• 2 month	0.4 ± 0.8	0.8 ± 1.8	0.3 ± 0.6
• 3 month	0.8 ± 1.7	1.0 ± 1.6	0.7 ± 1.4
Schirmer scores (mm/5 min)			
• Baseline	14.9 ± 10.3	10.3 ± 7.2	11.6 ± 10.5
• 1 month	15.4 ± 10.1	12.9 ± 9.1	10.1 ± 8.5
• 2 month	15.8 ± 9.4	12.4 ± 8.4	10.8 ± 6.4
• 3 month	12.3 ± 7.1	10.1 ± 6.0	9.6 ± 5.5
Tear breakup time (seconds)			
• Baseline	6.6 ± 2.2	5.4 ± 1.5	5.7 ± 3.3
• 1 month	8.0 ± 3.6	6.1 ± 2.8	7.4 ± 3.7
• 2 month	7.7 ± 3.1	6.2 ± 2.2	7.1 ± 3.4
• 3 month	7.7 ± 2.5	6.1 ± 2.4	7.3 ± 3.6
Tear osmolarity			
• Baseline	295.5 ± 17.4	311.3 ± 19.8	306.9 ± 28.4
• 1 month	304.4 ± 30.1	307.7 ± 17.3	307.9 ± 24.2
• 2 month	303.9 ± 22.1	300.1 ± 19.2	295.3 ± 20.7
• 3 month	299.5 ± 16.2	304.4 ± 28.7	304.6 ± 19.6
Meibomian gland scores			
• Baseline	8.7 ± 2.4	7.1 ± 2.1	9.2 ± 2.6
• 1 month	7.6 ± 1.8	6.7 ± 2.5	7.2 ± 1.4
• 2 month	8.3 ± 2.0	6.3 ± 2.6	8.2 ± 2.2
• 3 month	8.7 ± 2.0	6.0 ± 2.3	7.3 ± 1.4

**Table 2.** Results of clinical parameters are summarized with the mean and standard deviation demonstrated at weeks 4, 8 and 12 in comparison to baseline.
